### **Potential Benefits of the Proposed Research to Human Subjects and Others**

There are no known potential benefits for the participants. However, research has shown that allowing patients to narrate stories about their serious illness has improved well-being for this patient population. The risks to the participants are minimal in comparison to the potential for generation of new knowledge about patient-centered palliative care narrative interventions for patients living with serious illness. We have outlined procedures to minimize the risks to participants, which are primarily psychological in nature. These procedures include reiterating the voluntary nature of the study and the participant’s ability to withdraw consent at anytime throughout study, having available appropriate referral contact information for supportive personnel for any moderate/severe psychological distress, and taking steps to ensure data security.

### **E. Potential Problems and Alternative Strategies**

**Patient burden.** Thinking and conversing about end-of-life preferences and overall QoL may initially distress some patients and families. Some patients may decide not to participate because these issues are too difficult to deal with in the context of their illness. Further, there is a plan in place for referral to appropriate follow-up services as needed. During the K99 phase, no participants required referrals, and no participants reported feeling that the intervention was too burdensome

**Nonresponse bias and recruitment and attrition.** Patients who participate may differ from those who decline. Data on response rates will be collected and non-respondent characteristics will be examined to estimate the magnitude of any potential nonresponse bias. To decrease concerns about attrition, the study design calls for only a one-week period from enrollment to follow-up data collection. In addition, as described above, we will use an intention-to-treat analysis and modern missing data approaches. During the K99, all enrolled patient participants completed data collection, and only 2 nurse participants were recruitment failures. One nurse participant unenrolled because of a personal family emergency. The other nurse, an outside temporary agency RN, was unable to be contacted. If we cannot recruit a nurse, the patient's data will still be included in outcome and process analyses, which will inform study procedures in the larger trial.

**Blinding and contamination of intervention effects.** Although the R00 study will use computer-randomized assignment to the intervention and usual care groups, given the patient-centered intervention and patient-reported outcomes, it will not be feasible to blind participants (patients or nurses). Future studies could have an active control and blinded outcome assessment to help address this limitation. In the proposed R00 study, it is possible that the nurses may naturally demonstrate improved communication based on their knowledge of the study. To address this possible contamination, future studies could use a cluster randomized design with clinics or healthcare institutions, rather than patients, as the unit of randomization.

## F. Data Analysis Plan.

**Aim 1 Analysis Plan.** Statistical analyses will be performed with the use of SAS software, version 9.4. In preliminary analyses, data will be screened for errors and outliers; appropriate transformations will be made for non-normal outcomes. Baseline demographics will be summarized using standard descriptive statistics. The pattern of participant dropout will be examined to ensure a reasonable equal distribution of participants lost to follow-up between groups and based on baseline characteristics. Maximum likelihood techniques will include participants with incomplete data without need for imputation. In addition, we will conduct sensitivity analyses to examine the effect of departures from key assumptions made in the main analysis and to help determine effects of missing data. Using an intent-to-treat approach, primary and secondary outcomes will be analyzed with linear mixed models using SAS Proc Mixed to compare the two groups (narrative intervention versus usual care) over the assessment period. Separate models will be estimated for each of the primary and secondary outcomes, though relationships among outcomes will also be assessed. Mixed models will specify intervention group and time as fixed effects and subject as a random effect. Pairwise comparisons testing group effects at each time point are proposed to disentangle the effects of intervention process versus change in quality of communication between patient and nurse. All statistical analyses will be done in consultation with the project statistician, [name].

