**Sample Size and Power Analysis.** Sample size estimates were generated to determine power to detect a time by treatment interaction within the proposed repeated measures design. Assuming two-sided alpha = 0.05, a sample size of 80 patients will provide 80% power to detect an effect size associated with treatment effects on changes over time as small as  $f=.14$  (Cohen's  $d = 0.28$ ). This represents a small, clinically relevant effect, but more importantly will provide stable measures of outcome means and standard deviations over time for use in the planned R01 efficacy trial. Modern missing data techniques will be used if patients drop out before all follow-up data is obtained. To minimize concerns for attrition, the time between baseline and follow-up data collection is small. Nonetheless, if patients are lost to follow-up, even if a high level of attrition (e.g., 20%) will allow for the detection of a small effect size of  $f=.16$ .

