**Psychological.** For the patient participants, there is minor/moderate/severe risk for psychological distress due to the sensitive topics of serious illness. We will assure that participants understand both orally and in writing that they are free to decline participation in any and all study activities at any time, including declining to answer specific questions, refusing participation in the intervention, requests to speak off the record, or complete withdrawal from the study. If any of the interview or psychometric assessment data reveal increased participant distress, dissatisfaction or any adverse event, the data collection will cease. If the participant exhibits any verbal or non-verbal distress, the research team member will allow the participant to stop the interview, reschedule for return visit to complete interview, or allow participant to withdraw consent. If moderate distress is exhibited, the research team member will assist in referring participant to emotional support either through family, friends, or the healthcare team for follow-up related to the participant's distress. If severe distress, such as noting suicidal ideation, the research team member will immediately refer patient for further work-up and care. The research team member will carry a list of contact phone numbers for such referrals. If any moderate or severe distress is noted, this will be reported immediately to the PI for help in determining if the event meets criteria for a reportable adverse event. If deemed serious adverse event, the IRB will be notified and the participant's involvement in the research study will be discontinued. Patient or nurse participants will be able to contact the PI to discuss any concerns or questions at any time during their participation in the study. In a previous study using this methodology, none of these adverse events occurred. Therefore, we anticipate these risks to be rare events given the nature of the data collection procedures.

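### Psychological distress is the plan's main named harm, yet no planned analysis summarises distress events, and the patients affected may be missing from the outcomes that are analysed

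*Combined protocol and SAP*

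**What the plan says.** **The harm.** Section IV.D, c. Potential Risks (Psychological), states that "there is minor/moderate/severe risk for psychological distress due to the sensitive topics of serious illness". The section on potential benefits adds: "We have outlined procedures to minimize the risks to participants, which are primarily psychological in nature". Section IV.E (Patient burden) accepts that the topics may at first upset some patients.

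**Handling.** Distress is managed case by case, with stopping, rescheduling, withdrawal or referral. On reporting: "If any moderate or severe distress is noted, this will be reported immediately to the PI". Serious events go to the IRB and the participant is discontinued. The same paragraph says data collection ceases if interview or questionnaire data reveal increased distress.

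**Analysis.** Section IV.F (Aim 1) says: "Using an intent-to-treat approach, primary and secondary outcomes will be analyzed with linear mixed models using SAS Proc Mixed to compare the two groups". It adds pairwise group comparisons at each time point, a check of dropout by group, and sensitivity analyses for missing data. PROMIS anxiety, depression and negative illness impact enter only as secondary outcomes in these models. Under Randomization and Demographics (IV.C), the only further summary of outcomes is subgroup means and SDs. Aim 2 codes exit interviews thematically for barriers and facilitators. No section tabulates distress reports, referrals or discontinuations.

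**The concern.** The protocol itself expects distress in some patients, not as a shift of the whole arm. The plan records the relevant events, since staff must report them, but then leaves them out of its results. What remains between arms is a set of PROMIS means, in which a minority's worsening is diluted. The affected patients may also be the ones without later scores, because data collection ceases on distress and participation ends after a serious event. The exit interviews can lose the same patients.

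At stake is what this proof-of-concept study passes on to the planned efficacy trial. Followed as written, it could report acceptability themes and mean scores without stating how many patients in each arm were distressed, referred or stopped.

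**Working it through.** **1. The plan's own power figure.** The Sample Size paragraph states "Assuming two-sided alpha = 0.05" and "a sample size of 80 patients will provide 80% power to detect an effect size" of f = 0.14, or f = 0.16 after 20% attrition (N = 64). Take the interaction F test with 2 arms, m = 3 visits, λ = f²·N·m/(1−ρ), and df 2 and 2(N−2). The plan gives no visit correlation; ρ = 0.5 is assumed.
- N = 80: λ = 0.0196 × 80 × 3 / 0.5 = 9.41; power 78.2%.
- N = 64: λ = 0.0256 × 64 × 3 / 0.5 = 9.83; power 79.8%.

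Both reproduce the stated 80% within 2 points. For f = 0.14 and N = 80, power runs from 62.7% (ρ = 0.3) to 94.9% (ρ = 0.7).

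**2. Dilution of harm in the mean.** If a share p worsens by h SD and the rest improve by b SD, the mean shift is p·h − (1−p)·b. All values of p, h and b are assumptions. With no change at baseline and the same shift at both follow-ups, f = 0.2357 × shift.

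| p | h | b | Mean shift (SD) | Interaction power, ρ = 0.5 (0.3 to 0.7) |
|---|---|---|---|---|
| 10% | 1 | 0 | +0.10 | 7% (6–8%) |
| 15% | 1 | 0 | +0.15 | 10% (8–13%) |
| 20% | 1.5 | 0 | +0.30 | 26% (20–41%) |
| 15% | 1 | 0.2 | 0.15 − 0.17 = −0.02 | 5% |
| 10% | 1 | 0.3 | 0.10 − 0.27 = −0.17 | 11% (9–16%), in the direction of benefit |

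**3. Loss of the harmed patients.** If every harmed patient lacks later scores, the shift among those still measured is −b. With p = 15%, h = 1 and b = 0.2 it moves from −0.02 to −0.20 SD. In a complete-case simulation (40 per arm, ρ = 0.5) the estimate then favours the intervention in about 84% of trials, against 54% without the loss. With b = 0 the shift moves from +0.15 to 0. Maximum likelihood does not recover the lost harm unless the observed scores predict who was harmed.

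**4. Would a count of worsened patients do better?** Take ρ = 0.5, so the SD of change is √(2 × 0.5) = 1 SD, and a margin of 0.5 SD. Usual care: P(Z > 0.5) = 30.9%. Intervention with p = 15%, h = 1, b = 0.2: 0.15 × P(Z > −0.5) + 0.85 × P(Z > 0.7) = 0.15 × 0.691 + 0.85 × 0.242 = 30.9%. The two arms tie.

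A simulation used 40 per arm, SD 10, ρ 0.5–0.7, 10–15% worse by 10 points, and margins of 3, 5 or 10 points.
- Rest unchanged: the count signals harm in about 5–13% of trials; the baseline-adjusted mean comparison does so in 7–14%.
- Rest improving by 2 points: about 1–7% against 1–2%. The count shows no excess in the intervention arm in about 41–67% of trials.

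**5. What an event table would show.** Exact two-sided 95% limits: 0/40 gives an upper limit of 1 − 0.025^(1/40) = 8.8%; 4/40 gives 2.8–23.7%. At a true rate of 5%, the chance of at least one event among 40 is 1 − 0.95^40 = 87%. A between-arm test stays weak: 32% power for 5% against 15% (assumed rates).

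**6. Is distress ascertained alike in both arms?** The documents disagree.
- IV.D a, data collection by group: usual care is assessed at baseline and once more, and the interviews are listed for the intervention arm only.
- IV.C Measures and IV.D b, Quantitative Data: all patients are assessed three times.
- IV.D a, Patients: each patient has two recorded interviews. IV.D b, Qualitative Data, counts 80 narrative and 80 patient exit interviews.

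**The case against.** **Distress is already managed.** True: cases are referred, reported to the PI and, if serious, to the IRB. It can also surface in exit interviews, and IV.F examines dropout by group and promises sensitivity analyses. A reader might infer that the plan ignores distress; it does not. But none of these provisions yields a rate by arm, and the missing-data checks are not tied to distress.

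**Data collection may only pause.** The same paragraph allows rescheduling, so missing later scores are possible, not certain. This stands, and is why the point says may.

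**A better scale exists.** A reader might infer that counting individual PROMIS worsening would reveal what the means hide. Step 4 does not support that: at 40 per arm it can miss the same harm.

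**The expectation of rarity is unsupported.** The protocol says: "Therefore, we anticipate these risks to be rare events given the nature of the data collection procedures". A reader might set against this the K99 phase, in which none of 20 patients needed referral. That is a count of referrals, not of distressed patients, and the other study cited has no denominator. The sentence states an expectation in a risk section; no edit to it follows.

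**This is an 80-patient pilot described as minimal risk.** It cannot test safety. That limits the remedy to description but does not remove the gap.

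**Conclusion.** The gap is established by the text: the main named harm has no planned summary. The consequence is that the planned means and themes would most likely understate harm confined to a minority. Its size depends on assumed inputs: about 7–10% interaction power when 10–15% worsen by 1 SD at ρ = 0.5, and 26% when 20% worsen by 1.5 SD.

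A reader might go further and conclude that such harm would be reported as no effect or as benefit. The documents do not support so firm a claim. A frequent and large harm could show, and an apparent benefit requires the other patients to improve or the harmed patients to be lost. No document supplies those shares or sizes.

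This is a cheap reporting improvement, not an error that invalidates Aim 1.

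**What to change.** First reconcile the statements on usual-care assessments and on who is interviewed (working, step 6). They decide whether distress is ascertained alike in both arms and over what shared window.

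Then add to Section IV.F:
- A descriptive table, by arm, of moderate and severe distress reports, referrals and distress-related discontinuations, with exact 95% intervals. List events noted only at interviews separately.
- A separate row for patients with a distress event and no later PROMIS score, and their inclusion in the sensitivity analyses already promised.
- Optionally, the distribution of individual changes in anxiety, depression and negative illness impact as supporting description. A count beyond a worsening margin should not be presented as a more sensitive measure of harm.

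No distress-handling rule changes. The cost is a paragraph and one table, built from events already reported to the PI, provided each is logged with its severity, date and setting. The downside is wide intervals at 40 per arm.

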**Randomization.** Randomization to the narrative intervention or usual care will occur at the patient level. The random allocation sequence will be computer generated using random block sizes, an allocation ratio of 1:1, and stratification by illness group. The project statistician will generate the allocation sequence using SAS software and the allocation sequence will be uploaded for study use into REDCap. Upon study completion, baseline characteristics between intervention and control patients will be compared using independent samples t-tests (continuous measures) and chi-square tests (categorical measures). Though balance is assumed, statistical adjustment will be used in outcome analyses in the event of pre-treatment differences between conditions.

**Data collection.** All survey and demographic data will be captured using electronic surveys through REDCap on password-protected iPads/laptops.

**Demographics.** At baseline, age, gender, race/ethnicity, education in years, income level, religion/spirituality preference, and clinical details to identify co-morbidities and severity of illness will be collected for all participating patients. This demographic detail will allow description of outcome means and standard deviations in key patient subgroups, including groups defined by patient race/ethnicity and specific chronic illnesses of heart disease or end-stage renal disease.

**Measures.** For Aim 1, the primary and secondary outcome measures will be collected at three time points from all patient participants. (Table 1). The purpose of these times periods are to collect the outcome measures consistently for usual care and intervention participants. This is based on knowledge gained during the K99 study regarding time to complete the narrative intervention. In the K99 study, for the narrative intervention, on average it took 24 hours post narrative interview to upload the patient's narrative into the EHR.

**Exit Interviews and Usability Scale.** For Aim 2, the patient and nurse exit interviews and system usability surveys from the nurses will be collected approximately 1-week post intervention. (Table 1).

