Data collection activities for the nurse participants will include completing a 30-minute exit interview via an audio-recorded interview. For the usability testing, data collection will include testing of the EHR interface with the bedside nurses and completion of a short questionnaire at the end of the 30-minute exit interview.

The participants will be recruited through the University of Colorado Hospital.

b. *Sources of Materials*

*Qualitative Data.* For this proposed project, data will only be collected by the research team. Materials include audio recordings of interviews, field notes, and correspondence (i.e., memos, emails) with research

Instructions – How to complete the COMIRB protocol template (Social)

CF-184, Effective 4-26-2010

team members. A total of 240 audio-recorded interviews will be collected—80 interviews for the narrative intervention, 80 for the patient exit interviews, 80 for the nurse exit interviews.

**Quantitative Data.** All patients (intervention and usual care group) will complete a questionnaire at baseline, immediately post narrative upload in the EHR, and 24-48 hours post narrative upload. All survey data will be captured using electronic surveys through REDCap on password-protected iPads/laptops. After each participant's baseline data is collected by the professional research assistant, the participant will be randomized to be included in either the narrative intervention or usual care group. This randomization will occur with the randomization computer-generated algorithm. After the participant is randomized, a unique study identifier for all enrolled participants will be created for a de-identified data set.

Steps of de-identification:

1. The research team will assign the patient participant a de-identified code (i.e. P1) after consent is signed. This code will be the identifier throughout the study to link the narrative interview, the REDcap surveys, and the exit interview.
2. The research team will assign the nurse participant a de-identified code (i.e. N1) that corresponds numerically with the patient participant code.
3. For the REDCap survey data:
  - a. When each participant is added to the REDcap database, the research team will add this assigned de-identified code as the participant identifier.
  - b. Since the participant needs to take the survey three times, at the time of adding the de-identified code, the exact number of times they should take the survey will be added.

c. **Potential Risks**

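### The Aim 1 model sentence leaves out the group-by-time term on which the trial was sized, and baseline communication scores enter the follow-up group comparisons only conditionally

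*Combined protocol and SAP*

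**What the plan says.** Section IV.C, Sample Size and Power Analysis, bases N = 80 on "power to detect a time by treatment interaction within the proposed repeated measures design". It gives two-sided alpha 0.05, 80% power and f = .14, which it also labels d = 0.28. With 20% attrition the detectable effect becomes f = .16. It states no number of visits, degrees of freedom or within-patient correlation.

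Section F, Aim 1 Analysis Plan, gives the model: "Mixed models will specify intervention group and time as fixed effects and subject as a random effect". No interaction is listed. The next sentence reads: "Pairwise comparisons testing group effects at each time point are proposed to disentangle the effects of intervention process versus change in quality of communication". The section names no model term or time point as the deciding test for QOC, the primary outcome.

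On baseline, section IV.C, Randomization, plans tests of baseline characteristics between arms and then says that "statistical adjustment will be used in outcome analyses in the event of pre-treatment differences between conditions". It names no variable and sets no trigger. Section D, Sources of Materials, fixes the order of events: once "baseline data is collected by the professional research assistant, the participant will be randomized", so Time 1 precedes allocation.

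The number of assessments is inconsistent. Table 1, the Measures paragraph of section IV.C and Sources of Materials give all patients three. The usual care paragraph in section D gives that arm two.

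**The concern.** The analysis section is what gets programmed. A model with group and time as the only fixed effects forces the group difference to be the same at every visit. It therefore cannot test whether the arms change differently over time, which is the hypothesis that was powered, and it cannot give a separate group effect at each visit, which the following sentence requires. Its single group coefficient also averages in a visit at which no treatment effect can exist.

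Two smaller gaps remain after the term is added. First, with complete data and group-by-time in the model, the Time 2 and Time 3 group comparisons are raw differences in means, so baseline QOC sharpens them only if the conditional adjustment is invoked. Second, a reader cannot tell from section F whether the interaction, Time 2 or Time 3 decides the primary outcome.

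**Working it through.** **Inputs.** From the documents: N = 80 at 1:1 (40 per arm), two-sided alpha 0.05, f = .14 (N = 80) and f = .16 (20% attrition, N = 64), three time points. Assumed: SD 1 at each visit, equal correlation ρ between visits (0.3/0.5/0.7 shown), complete data, and Time 1 as a response in the model.

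**1. The plan's own figure.** For a two-arm, m-visit interaction, λ = f²·N·m/(1−ρ), with df (m−1) and (N−2)(m−1).
- m = 3, ρ = 0.5, N = 80, f = .14: λ = 0.0196 × 80 × 3/0.5 = 9.41, df 2 and 156, power 78.2% (80% needs f = .143).
- m = 3, ρ = 0.5, N = 64, f = .16: λ = 9.83, power 79.8%.
- m = 2, ρ = 0.6: N = 80, f = .14 gives λ = 7.84 and power 79.0%; N = 64, f = .16 gives λ = 8.19 and 80.4%.

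The stated figures are reproducible, but from more than one design.

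**2. What f = .14 means at follow-up.** For group differences Δ at the visits, f² = mean[(Δ−mean Δ)²]/4.

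| Pattern of Δ | f | Largest difference at f = .14 |
|---|---|---|
| (0, d, d) or (0, 0, d) | d/√18 | 0.594 SD |
| (0, d/2, d) or (0, d, d/2) | d/√24 | 0.686 SD |
| two visits (0, d) | d/4 | 0.56 SD |

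The label d = 0.28 is 2 × .14. A true 0.28 SD difference at one visit, unadjusted with 40 per arm, has 23.5% power.

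**3. Literal model against the interaction, 0.594 SD.** The literal group coefficient estimates mean(Δ), with SE = √[(2/40)(1+2ρ)/3] = 0.163/0.183/0.200 and 78 df. For (0, d, d) it estimates (2/3) × 0.594 = 0.396 SD; for (0, 0, d) it estimates 0.594/3 = 0.198 SD.

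| Power | ρ = 0.3 | ρ = 0.5 | ρ = 0.7 |
|---|---|---|---|
| Interaction (either pattern) | 63% | 78% | 95% |
| Literal group test, effect at Times 2 and 3 | 67% | 57% | 50% |
| Literal group test, effect at Time 3 only | 22% | 19% | 16% |

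For the equal-effect pattern the two tests cross at ρ of about 0.33; below that the literal test is slightly better.

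**4. Baseline in the Time 3 comparison, 0.594 SD.** Unadjusted SE = √(2/40) = 0.224, 78 df: power 75%. Baseline-adjusted SE = √[(2/40)(1−ρ²)] = 0.213/0.194/0.160, 77 df: power 79/86/96%. The gain is worth 40/(1−ρ²) = 44/53/78 patients per arm instead of 40.

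**The case against.** The strongest reply is that this is an omission and not a contradiction. The sample size paragraph names the interaction, group effects at each time point cannot be produced without it, and the analyses are to be done in consultation with the project statistician, so the additive model may never be fitted. That is fair as to intent, and the cost does depend on an unstated correlation: at ρ = 0.3 with equal follow-up effects the literal test loses nothing. It does not make the written model right.

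It is also true that this is a proof-of-concept study. The sample size paragraph ranks detection below the aim that the sample "will provide stable measures of outcome means and standard deviations over time for use in the planned R01 efficacy trial". Per-visit means and SDs are unaffected by the model wording. Unadjusted randomized comparisons are valid, so the baseline issue is one of precision. Time 1 QOC, as a repeated outcome, already informs the interaction and, under maximum likelihood, enters the follow-up contrasts to some extent when data are missing.

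Several stronger readings are tempting and not supported:
- That the power paragraph fixes a three-visit, 2-df test. A two-visit test at ρ = 0.6 fits its figures as well.
- That f = .14 simply means 0.594 SD at follow-up. This holds only for a flat or single-visit effect over three visits.
- That adjustment hangs on a significance test of baseline QOC. Neither QOC nor a threshold is named.
- That the false-positive rate is inflated. It would be about 8 to 10% if Time 2 and Time 3 were each taken as deciding, but the documents do not say that.

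**Conclusion.** The concern holds as a specification fault in section F that should be fixed. The model as written cannot deliver the powered test or the visit-specific comparisons promised beside it. For an effect matching f = .14 at ρ = 0.5, fitting it literally would cost about 21 points of power if the effect is equal at both follow-ups (78% to 57%) and about 59 points if it appears only at Time 3 (78% to 19%). These sizes rest on the assumed correlation, constant SD and complete data.

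Conditional use of baseline is a lesser matter: a valid analysis that gives up 4 to 21 points of power at Time 3 over ρ of 0.3 to 0.7. The unnamed deciding test is secondary. Nothing here shows the sample size to be wrong.

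**What to change.** First reconcile the two-assessment schedule for usual care in section D with the three assessments in Table 1, Measures and Sources of Materials. A Time 3 contrast needs data from both arms. Then:

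1. Add group-by-time to the model sentence in section F.
2. Use baseline QOC in the Time 2 and Time 3 comparisons whether or not the arms differ, through a common baseline mean for both arms or as a covariate. Drop the Time 1 group test, since there is no treatment effect to find before randomization.
3. In the same edit, name one QOC test as deciding and make the other time-point comparisons secondary. The choice is the sponsor's.
4. If the effect size is annotated, say only that d = 0.28 is 2f and not a 0.28 SD follow-up difference. Add that the follow-up difference matching f = .14 depends on the effect pattern and number of visits (about 0.56 to 0.69 SD in the patterns checked).

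The cost of the analysis changes is a few lines of plan text and SAS code. They need no additional measurements, and N stays at 80.

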**Table 1. Outcome Data**

Participant	Time 1: Baseline	Time 2: 24-48 hours post baseline/narrative upload	Time 3: 24-48 hrs after Time 2	1- week Post Upload
Patient	1. Quality of Communication(19)* 2. PROMIS-29 Profile:v2.1(29)* 3. PROMIS Psychosocial Illness Impact a)Positive affect (8)* b) Negative affect (8)* 4. Demographics	1. Quality of communication(19)* 2. PROMIS-29 Profile:v2.1 (29)* 3. PROMIS Psychosocial Illness Impact a)Positive affect (8)* b) Negative affect (8)*	1. Quality of communication(19)* 2. PROMIS-29 Profile:v2.1 (29)* 3. PROMIS Psychosocial Illness Impact a)Positive affect (8)* b) Negative affect (8)*	
Nurse				System Usability Scale (10)*
Pt/Nurse				Exit Interviews

\*(n)= number of items in outcome measure

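### A subject random effect alone imposes one variance and one correlation on all three visits; change contrasts and at-visit comparisons lose calibration if that is wrong, though the powered interaction test does not

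*Combined protocol and SAP*

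**What the plan says.** The Aim 1 analysis plan (section IV.F) analyses each primary and secondary outcome with a linear mixed model in SAS Proc Mixed, by intention to treat, using maximum likelihood for incomplete data. The covariance specification is this sentence: "Mixed models will specify intervention group and time as fixed effects and subject as a random effect". No residual covariance structure, random slope, robust standard error or degrees-of-freedom method is named. The same section plans pairwise group comparisons at each time point. It also promises sensitivity analyses for departures from key assumptions, without naming the covariance among them.

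The Sample Size and Power Analysis paragraph (section IV.C) computes "power to detect a time by treatment interaction within the proposed repeated measures design" and describes its effect size as one for "treatment effects on changes over time". It states no within-patient correlation.

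Under Measures in section IV.C, "the primary and secondary outcome measures will be collected at three time points from all patient participants". Table 1 puts Time 2 at 24-48 hours after baseline or upload and has "Time 3: 24-48 hrs after Time 2", so the assessments span roughly 2-4 days.

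**The concern.** A random intercept with independent residuals is compound symmetry. It makes two restrictions: the outcome variance is the same at every visit, and the baseline-to-Time 3 correlation equals the correlation between adjacent visits. Neither is supported by a figure in the documents.

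If the correlation restriction fails, every change contrast gets a standard error built from the average correlation. The least correlated pair (baseline and Time 3) gets one that is too small, and adjacent pairs get one that is too large. If the variance restriction fails, every at-visit group comparison uses the average variance. It is then too liberal where scores are more variable and too conservative where they are less so.

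The time-specific results are meant to separate the effect of the intervention process from a change in communication with the nurse. Time 3 is the assessment furthest from upload, so the calibration of results at that visit matters for interpretation. The study is also meant to supply outcome SDs over time for the next trial, and a model with one common variance does not report them by visit.

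**Working it through.** **Inputs from the documents.** "Assuming two-sided alpha = 0.05, a sample size of 80 patients will provide 80% power"; f = .14 at N = 80 and f = .16 after 20% attrition (N = 64); "an allocation ratio of 1:1, and stratification by illness group", hence 40 per arm; three visits.

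**Assumed inputs.** All correlations and visit SDs. Data are complete and balanced, and a group-by-time term is fitted. The model sentence does not list that term, but both the powered test and the at-visit comparisons need it.

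**Step 1. The plan's own power figure.** For a within-between interaction with k = 2 groups, m = 3 visits and correlation rho, take lambda = f² × N × m / (1 − rho), df1 = (k−1)(m−1) = 2 and df2 = (N−k)(m−1). With rho = 0.5 and equal correlations assumed:

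- N = 80, f = .14: lambda = 0.0196 × 80 × 3 / 0.5 = 9.41, df2 = 156, power 78.2%. The f detectable at 80% is .143, which rounds to .14.
- N = 64, f = .16: lambda = 0.0256 × 64 × 3 / 0.5 = 9.83, df2 = 124, power 79.8%. The detectable f is .160.

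The stated figures are therefore reproduced under an equal-correlation assumption.

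**Step 2. Change contrasts when correlation falls with time, equal visit variances.** The model takes the variance of a within-patient change as 2σ²(1 − r̄), where r̄ is the mean of the three pairwise correlations. The true value is 2σ²(1 − r_jk). So

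SE ratio (model/true) = √[(1 − r̄)/(1 − r_jk)], and actual type I error = 2[1 − Φ(1.96 × ratio)].

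Worked case, correlations .7/.7/.49 (Times 1-2, 2-3, 1-3): r̄ = 1.89/3 = .63.

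- Time 3 minus baseline: √(.37/.51) = 0.852; 1.96 × 0.852 = 1.67; type I error 9.5%.
- Time 2 minus baseline: √(.37/.30) = 1.111; 1.96 × 1.111 = 2.18; type I error 3.0%.

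| Assumed correlations (1-2 / 2-3 / 1-3) | Time 3 − baseline: SE ratio, type I error | Time 2 − baseline: SE ratio, type I error |
|---|---|---|
| .5/.5/.5 | 1.00, 5.0% | 1.00, 5.0% |
| .7/.7/.65 | 0.95, 6.2% | 1.03, 4.4% |
| .6/.6/.5 | 0.93, 6.8% | 1.04, 4.1% |
| .7/.7/.6 | 0.91, 7.4% | 1.05, 3.9% |
| .5/.5/.25 | 0.88, 8.4% | 1.08, 3.4% |
| .7/.7/.49 | 0.85, 9.5% | 1.11, 3.0% |
| .8/.8/.64 | 0.84, 10.0% | 1.13, 2.7% |

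Simulation (40,000 null trials per pattern, 40 per arm) agrees with these values. When each contrast uses its own variance, as an unstructured model does with complete data, type I error is 4.8-5.2%.

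**Step 3. The tests that the plan names, under the same decay.** The joint 2-df interaction test from the random-intercept model runs at 5.0-5.7% in simulation. Group comparisons at a single visit run at 4.8-5.0% when visit variances are equal, because their standard error does not involve the correlation between visits.

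**Step 4. At-visit comparisons when visit SDs differ.** In balanced data the model uses the mean of the visit variances at every visit. With assumed SDs 1.0, 1.1 and 1.2, the mean is (1.00 + 1.21 + 1.44)/3 = 1.217.

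- Time 3: √(1.217/1.44) = 0.919; 1.96 × 0.919 = 1.80; type I error 7.2%.
- Time 2: √(1.217/1.21) = 1.003; type I error 4.9%.
- Baseline: √(1.217/1.00) = 1.103; 1.96 × 1.103 = 2.16; type I error 3.1%.

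Simulation gives 6.8-7.1% at Time 3 and 3.0% at baseline. Using each visit's own variance restores 4.9-5.1%.

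**The case against.** The strongest reply is that the inference the study is powered on does not suffer. The effect size in the power paragraph belongs to the time-by-treatment interaction, a 2-df test with three visits, and that test stays near 5% under every pattern tried. Section IV.F lists group comparisons at each visit and no Time 3 minus baseline contrast; those comparisons hold their level when visit variances are equal. A reader might infer that the trial's main test is inflated, or that the later effect would be declared significant too often. The documents do not support either inference. This part of the reply stands.

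It also stands that the documents give no correlations. With visits only days apart the decay may be slight, so the lower end of the range (about 6-7% for Time 3 minus baseline) may be nearer the truth than 9-10%. With complete balanced data the estimated means and mean changes are the same under either covariance; only their standard errors differ.

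Two further replies carry less weight. The sentence does not rule out an added residual structure, but none is written, and an analyst following it would fit compound symmetry. The promised sensitivity analyses do not name the covariance, and would leave the main analysis's standard errors unchanged. Nor does the at-visit defence survive unequal visit variances, as Step 4 shows for a comparison the plan does name.

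**Conclusion.** The concern holds in a limited, conditional form. The written model imposes one variance and one correlation over three visits, with nothing in the documents to support either restriction.

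- If correlation falls with time, individual change contrasts are miscalibrated: about 6-10% for Time 3 minus baseline and about 3-4% for Time 2 minus baseline, at a nominal 5%.
- If visit SDs drift modestly (1.0/1.1/1.2 assumed), the planned at-visit group comparison runs at about 7% at the most variable visit and about 3% at the least variable.
- The powered interaction test stays at 5.0-5.7%.
- If correlations and variances are equal, there is no error at all.

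These figures assume complete data with 40 per arm; the effect of a wrong covariance under dropout was not computed. This is a cheap improvement to a concrete but restrictive specification, not a flaw that invalidates the primary analysis.

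**What to change.** In section IV.F, replace the subject random effect with a REPEATED statement for visit within patient, TYPE=UN, fitted by REML with Kenward-Roger degrees of freedom. Name a simpler fallback structure in advance in case the model does not converge. In the same sentence, list the group-by-time term and say which contrasts will be reported (at-visit differences, changes from baseline, or both).

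The cost is one line of code and a sentence or two of text. The unstructured matrix has six parameters, which 80 patients with three visits can support. The downside is a slight loss of degrees of freedom if compound symmetry is in fact true. The visit-specific variances and correlations it estimates are also useful for planning the efficacy trial.

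One related passage must be reconciled first. Section IV.D describes outcome collection for usual care at baseline and 24-48 hours after enrolment only, whereas Table 1, the Measures paragraph and the Quantitative Data paragraph give three assessments in both arms. Any Time 3 group contrast needs Time 3 data from usual care.
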